In an innovative use of an established and well validated intervention for insomnia, we propose to examine the direct effects of sleep on biomarkers of CVD risk outcomes among persons with PTSD and comorbid insomnia disorder (ID; see Figure 1). In this 2-arm RCT, 150 participants with PTSD and ID will be randomized at a 2:1 ratio to either CBT-I, or a minimal contact control condition (CCC). We anticipate that we may need to consent and screen as many as 500 participants to reach this goal. Sleep efficiency as measured by actigraphy will be the primary sleep outcome measure. Other parameters [total sleep time (TST) wake after sleep onset (WASO), sleep fragmentation] will be measured with a multi-modal assessment strategy including validated self-report measures, sleep diaries collected *via* Qualtrics, and objective sleep measurement (i.e., actigraphy). Sleep diaries and actigraphy will be continuously collected for 10-weeks (including a week-long baseline, 8-week period for CBT-I or CCC, and one-week post treatment) and for a week-long period at the 6-month follow-up. The primary outcomes for this clinical trial are established biomarkers of CVD risk, including flow mediated dilation, SNS activity, nighttime BP, nighttime BP dipping, and ASCVD risk. These biomarkers will be assessed at three time points: baseline, post-intervention (8-weeks), and 6-month follow-up. The 6-month follow-up period will allow us to evaluate whether the intervention effects on CVD risk are sustained beyond the immediate post-intervention period. Timing for the 6-month follow-up visit will be 6 months after

the baseline assessment or three months after the post-intervention assessment, whichever is later. Participants in both arms will continue with usual medical care.

C.2. Recruitment

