During the study, study staff members will communicate with participants via phone, email, standard mail, or texts sent from a Duke-owned phone, based on participant preferences. Participants will be allowed to opt out of texting or emailing if they wish.

C.4. Interventions

C.4.1. Cognitive Behavior Therapy for Insomnia (CBT-I). The approach to CBT-I for the proposed study is based on CBT-I programs that have been practiced and studied by research team members (Karlin, Trockel, Tylor, Gimeno, & Manber, 2013; Manber, Carney, & Edinger, 2012). CBT-I is manualized in a session-by-session guide (Perlis, Jungquist, Smith, & Posner, 2005). [name] serves as a consultant and trainer on the nationwide dissemination of CBT-I. [name] will train study therapists to deliver CBT-I in accordance with the training approach adopted by the CBT-I dissemination effort (Karlin, Trockel, Tylor, Gimeno, & Manber, 2013). Further, [name] will be available for consultation regarding the training procedures and fidelity measures and methods.

C.4.2. Minimal Contact Control Condition. Participants assigned to the CCC will be contacted via WebEx or Zoom every week for eight weeks. To monitor their insomnia symptoms and mood, they will be asked to complete the PTSD Checklist and Insomnia Severity Index. Check-in calls will be audio-recorded. This will allow us to do fidelity ratings to ensure that participants are not receiving any sleep interventions, advice, etc. Please note that our lab has an SOP related to suicide risk assessment, and the study coordinator who makes the check-in calls has been trained in the use of the SOP. Participants

will be asked about any insomnia treatments they use/receive during usual care. At the end of the 6-month follow-up, participants randomized to this condition will be offered CBT-I.

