C.4.3. Intervention Training and Fidelity. Study therapists will include [name] and two masters' level mental health providers. Each therapist will provide treatment in both arms. Masters' level therapists will be trained by [name]. Initial didactic training (covering session by session procedures, core components of CBT-I and SH+) will last three days and be followed by training cases. Therapists will be allowed to provide the intervention once they have demonstrated 100% competence and adherence with all required treatment elements. Therapists will meet weekly for supervision throughout the trial. All therapy sessions will be audio-recorded. A random selection of twenty percent will be rated for fidelity. In order to protect against drift, the frequency of fidelity checks will occur equally across the beginning, middle, and end of the intervention period. [name] will rate therapist treatment fidelity/adherence for recorded sessions using the adapted version of the *Yale Adherence and Competence Scale* (Carroll, 2000). In the CBT-I condition, recordings will be rated on the presence/absence of CBT-I elements. In the comparison condition, recordings will be rated on the presence of proscribed elements of CBT-I. In addition, recordings from both conditions will be rated on the presence/absence of nonspecific treatment elements (e.g., therapeutic alliance, patient expectancies). Feedback from fidelity checks will be provided to therapists. In addition, emergency procedures for suicidal and homicidal ideation have been well developed in our laboratory and these will be carefully followed for each participant. [name] will also provide consultation to [name].

C.5. Measures

We have experience assessing all the proposed measures and items discussed below. Table 1 summarizes the measures and the timepoints at which they are given.

Table 2. Study Measures					
Measure	Completer 1=[name] team, 2=[name] team	Time			
		Screen*	Baseline	PostTxt	6-Mon
Clinician Administered PTSD Scale	Trained interviewer ¹	X ²			
Structured Clinical Interview for DSM5	Trained interviewer ¹	X ²			
Duke Structured Interview for Sleep Disorders	Trained interviewer ²	X ¹			
Montreal Cognitive Assessment	Trained interviewer ¹	X ¹			
Traumatic Life Events Questionnaire	Participant	X ¹			
PTSD Checklist	Participant	X ¹	X	X	X
Beck Depression Inventory – II	Participant	X ¹	X	X	X
WHO Disability Assessment Schedule	Participant	X ¹			
WHO Quality of Life	Participant		X	X	X

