C.7.2. Potential Benefits. While participants may benefit from improved sleep and/or reduced insomnia complaints, there are no guaranteed benefits to the individual participant and no immediate benefits of the proposed research to others. Information gathered from participants may help us to establish a link between sleep impairment and autonomic and inflammatory markers of CVD risk among individuals with PTSD. In our opinion, the anticipated benefits of this study outweigh the potential risks.

C.7.3. Protection from Risk. Participants are informed clearly during the initial informed consent process that the study is completely voluntary, and that they may refuse to answer any items that they do not wish to answer on the questionnaires and interviews. They are also informed that they are free to decline participation in any procedure and can withdraw from the study at any time. Potential risks will be minimized by carefully screening potential participants according to the inclusion/exclusion criteria, closely monitoring symptom levels, and following established laboratory procedures. Patients will complete the MoCA to assess cognitive function. Patients who score <20, which suggests the presence of cognitive impairment, will be informed of the results and encouraged to discuss the findings with their personal care physician for further evaluation and treatment if necessary. With regards to determination of decision making capacity of potential participants, our laboratory has a standard procedure for determining understanding of the study procedures, risks, and benefits. We utilize this procedure if we have any reason to suspect that the participant may have difficulty in the consent process (e.g., traumatic brain injury impacting cognitive function, active psychotic symptoms). In this procedure, the study coordinator providing the informed consent information evaluates understanding of the procedures at several different time points during the process by asking questions like “Do you understand what we’re asking you to do?” and “Do you have any questions about the risks of the study? Can you tell me what you understand the risks to be?”

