We believe that provision of treatment for insomnia should enhance rather than jeopardize health status, and potential serious adverse events (SAEs) for participants in this project are not expected. Regardless, we will minimize potential risk by carefully screening potential participants and following established laboratory procedures for physiological data acquisition and data safety monitoring. The individuals responsible for data safety and monitoring will be the PIs, the co-Investigators, and the study coordinator.

[name] will serve as the primary safety monitor for the proposed study. There will be several ongoing mechanisms for monitoring and reporting of adverse events (AEs), including serious adverse events (SAEs): 1) ongoing participant contact via study personnel; 2) a telephone number provided to participants to report concerns related to study participation; 3) weekly meetings between [name] and study personnel. In order to monitor possible adverse events, participants will be instructed to report any adverse effects of study participation as soon as possible to research staff; they will have contact information needed to report these problems to study personnel. The PI will meet at least weekly with study personnel to discuss participants' reactions to the intervention, proper delivery of the intervention, and any adverse events or unanticipated problems. Monthly meetings between the investigators and the study coordinator will allow for ongoing progress reports, including the number of participants currently involved in the study groups, attrition rates, and scheduled data collection from participants, as well as notification and review of any AEs. Safety monitoring for adverse events will be conducted in real time by [name] and/or study coordinator. The following information about adverse events will be collected: 1) the onset and resolution of the AE, 2) an

assessment of the severity or intensity, 3) an assessment of the relationship of the event to the study (definitely, probably, possibly or not related), and 4) action taken (e.g., none, referral to physician, start or increase concomitant medication). [name] will determine the severity of the event, will assign attribution to the event, and will monitor the event until its resolution.

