Any adverse events (AEs) will be reported to the Duke University Medical Center (DUMC) Institutional Review Board (IRB) in accordance with the local Human Research Protection Program's Standards of Practice. These guidelines require immediate reporting of any SAEs that are potentially study related. All research projects conducted at DUMC are required to have yearly IRB review. Reports of non-serious AEs or unanticipated problems that may increase risk for study participants or others are required as part of the annual progress reports. Additionally, any changes to the project between review periods must be approved by the IRB prior to implementation. All communication with the DUMC IRB will occur using Duke's electronic IRB system (IRIS).

C.7.6. Plans for Responding to Psychiatric Emergencies. Given the nature of PTSD symptoms, it is not unexpected that participants will experience increased distress associated with the assessment procedures and diagnostic clinical interviews. Our extensive clinical and research experience suggest that there is no serious risk in these patients associated with assessment and interview procedures as proposed. Over the past several years, several hundred patients with PTSD have participated in our research team's clinical trials, and there have been only rare occurrences of serious adverse events (i.e., hospitalization only) due to PTSD symptom increases.

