Calculations are based on Aims 1 and 2. Because each of the analyses will make use of repeated-measures data, statistical power will depend on the effective sample size (ESS). For Hypotheses 1, which will examine treatment effects associated with differences in sleep and cardiovascular outcomes, the ESS will be equivalent to the total number of observations (number of participants \times number of data collections) adjusted for intra-individual correlations. As the intra-individual, or intra-class, correlation (ICC) decreases, the ESS increases. Given that we anticipate substantial intra-individual variability on account of the intervention, an ICC of .50, representing an equal allotment of variance attributable to inter-individual differences and intra-individual variability, provides a conservative estimate of the ESS. With a sample of 150 contributing 3-time points of data each and an ICC of .50, the ESS would be 225. Even with 10% attrition post-intervention and then again at the 6-month follow-up, the ESS would be 215. Assuming equivalent attrition rates among the 100 CBT-I participants and 50 controls, this would have 80% power to detect treatment effects equivalent to Cohen's d of 0.41 via a two-tailed test with an alpha of .05. For reference, a meta-analysis on CBT-I (Okajima, Komada, & Inoue, 2011) found 12-month treatment effects on SOL, WASO, and sleep efficiency equivalent to $d = 0.45, 0.47$, and 0.54 , respectively. *Six-month follow-up CBT-I treatment effects in Talbot et al.'s (2014) RCT of CBT-I in persons with PTSD far exceeded these for SE ($d = 1.48$), SOL ($d = 1.31$), and TST ($d = 0.76$).* Moreover, Talbot et al. (2014) recorded large effects of CBT-I on 6-month increases in psychosocial functioning ($d = 1.02$). Although the specific impact of CBT-I on CVD risk remains untested, comparable behavioral-health interventions, such as stress management, have shown robust effects. For instance, in one study, 16 weeks of weekly 1.5-hour stress-management training compared to usual care was sufficient to achieve large increases in FMD ($d = 2.32$; Blumenthal,

[name] et al., 2005). In another study, a similar regimen of weekly group stress-management sessions was associated with significantly reduced time to adverse cardiac events, $HR = 0.26$ (95% CI: 0.07-0.90), in comparison to usual care. Given these effect sizes, the present study should have adequate power to detect treatment effects similar to those found in previous trials.

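### The PTSD Checklist and ISI are specified during the eight-week period for controls only, so questionnaire-based detection of worsening, and prior exposure to the ISI, differ by arm

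*Combined protocol and SAP*

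**What the plan says.** On the control arm, C.4.2 states: "Participants assigned to the CCC will be contacted via WebEx or Zoom every week for eight weeks". It continues: "To monitor their insomnia symptoms and mood, they will be asked to complete the PTSD Checklist and Insomnia Severity Index". The study coordinator who makes these calls is trained in the laboratory's SOP on suicide risk.

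On the CBT-I arm, C.4.1 describes the programme, the manual and therapist training. It names no symptom questionnaire at the sessions.

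C.5 introduces its table of measures with "Table 1 summarizes the measures and the timepoints at which they are given" (the table itself is captioned Table 2). It places the PTSD Checklist and the ISI at screening, baseline, post-treatment and 6 months. It has no column for the treatment period in either arm.

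On safety, C.7.3 lists among the protections for participants in general "closely monitoring symptom levels, and following established laboratory procedures". C.7.6 says of the team's past trials in PTSD that "there have been only rare occurrences of serious adverse events (i.e., hospitalization only) due to PTSD symptom increases". C.7.5 provides that "participants will be instructed to report any adverse effects of study participation as soon as possible to research staff", alongside continuing staff contact, a telephone line and weekly meetings.

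**The concern.** Two things are at stake.

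1. **Safety ascertainment.** C.7.3 offers close symptom monitoring as a protection without limiting it to one arm, and C.7.6 identifies PTSD symptom increase as the event the team has seen before. The PTSD Checklist is the study's own measure of PTSD symptom severity. As written, the arm receiving the intervention is the one without a scheduled score on it during the intervention.

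2. **Comparability of one outcome.** The ISI is both a monitoring tool in C.4.2 and part of the Hypothesis 1 manipulation check modelled in D.3. One arm would reach the post-treatment ISI having filled it in repeatedly over the preceding weeks, and the other would not. Repeated self-rating may shift later answers, and the treatment contrast cannot separate such a shift from the effect of CBT-I.

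The plan neither mentions this difference nor says how it would be handled.

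**Working it through.** **Arm sizes.** C.1 states that "150 participants with PTSD and ID will be randomized at a 2:1 ratio", which gives 150 × 2/3 = 100 CBT-I and 150 × 1/3 = 50 control. D.4 agrees: "Assuming equivalent attrition rates among the 100 CBT-I participants and 50 controls".

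**Scheduled PTSD Checklist and ISI scores (each instrument, per participant).** Inputs are C.4.2 for the weekly contacts and the C.5 measures table for the fixed assessments. The control figures assume completion at every weekly contact.

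| Period | Control | CBT-I |
|---|---|---|
| Baseline | 1 | 1 |
| Between baseline and post-treatment | up to 8 | 0 specified |
| Post-treatment | 1 | 1 |
| 6 months | 1 | 1 |
| Total, baseline to 6 months | up to 11 | 3 |

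Over the control arm this is up to 8 × 50 = 400 within-period administrations of each instrument. Over the 100 CBT-I participants, none is specified.

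**What does cover the CBT-I arm during treatment.**

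- Sleep diaries and actigraphy run continuously through the eight weeks in both arms (C.1, C.5.2.3). They record sleep, not PTSD symptoms.
- There are eight treatment sessions (C.7.8 reimbursement table), all audio-recorded, with weekly supervision of therapists (C.4.3). No symptom score is specified for them.
- Procedures for suicidal and homicidal ideation apply to every participant (C.4.3, C.7.6). They address acute risk rather than PTSD symptom severity.
- Adverse events are monitored in real time and reviewed at least weekly (C.7.5). This settles how reported events are handled, but not that both arms are asked the same question.

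So the gap is specific: a scheduled score on these two instruments, not observation as such.

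**Effect on the sample size.** None. D.4 uses 150 participants, three assessments and an ICC of 0.50.

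- Without attrition: ESS = 150 × 3 / (1 + 2 × 0.50) = 225, as stated.
- With 10% attrition at each step, 121.5, 13.5 and 15 participants give 3, 2 and 1 observations: 121.5 × 3/2 + 13.5 × 2/1.5 + 15 = 215.25, stated as 215.
- With a control ESS of 215/3 and a 2:1 ratio, power at d = 0.41 is 80.9%, against the stated 80%.

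The weekly control scores enter none of these figures.

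**The case against.** The strongest reply is that the documents show something unstated rather than something absent. The measures table omits the controls' own weekly questionnaires, and it has no treatment-period column for the continuous diaries and actigraphy either. Its silence about CBT-I sessions is therefore weak evidence. Session content is left to a manual that is not reproduced, and that manual may include symptom measures. C.4.2 also gives the frequency of contact, not of the forms. All of this stands. It is why the count reads 0 specified and up to 8, and why the first remedy is a statement in C.4.1.

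It can also be said that the questionnaires compensate controls for having no therapist. That is a reasonable motive, but it does not make the two forms of ascertainment equivalent.

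Several stronger readings are tempting, and the documents do not support them:

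- **That worsening goes unobserved under CBT-I.** The monitoring listed above contradicts this. The post-treatment PSQI also looks back over the past month (C.5.2.5).
- **That controls are untreated.** Usual medical care continues in both arms (C.1).
- **That adverse event capture is confined to what participants attribute to the study.** C.7.5 has other routes, and its relationship grading includes unrelated events.
- **That a PTSD Checklist comparison is biased.** D.3 names no such outcome in its analyses.

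**Conclusion.** The point holds as a difference in structured ascertainment: up to 8 scores per control participant against 0 specified per CBT-I participant during the intervention. It assumes that controls complete the forms at each weekly contact and that the CBT-I manual does not already include them.

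The consequences are limited. Questionnaire-based detection of PTSD or insomnia worsening is unequal between arms. The post-treatment ISI contrast carries a difference in prior administrations whose direction and size the documents do not allow one to state. Actigraphic sleep efficiency, which is the primary sleep outcome, and the cardiovascular biomarkers are not questionnaire scores, and nothing in the documents ties them to this difference.

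A reader might go on to infer that the safety results will favour CBT-I. That does not follow. Therapist sessions may detect as much as a check-in call or more, no change in either score is defined as an adverse event, and Section D plans no comparison of adverse events between arms. Nor can the difference be turned into a rate of missed worsening, because the documents give no incidence or duration for such episodes. This is an inexpensive improvement worth making, not a threat to the trial's main conclusions.

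**What to change.** 1. In C.4.1 and the measures table, schedule the PTSD Checklist and ISI at the CBT-I sessions at the frequency used for the control check-ins, with scores reviewed under the same SOP. If the sessions already include them, say so.
2. In C.4.2, state how often controls complete the two forms. Add a treatment-period column to the measures table showing both arms.
3. In C.7.5, specify one standard adverse event question, worded identically for both arms, at the existing weekly contacts.

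The cost is a small amendment and a few minutes of participant time at contacts that already take place. No extra visits or staff are needed, and the sample size is unchanged.
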